In addition to the self-report measures described above, we will measure gonorrhea and chlamydia by a real-time PCR assay for the direct, qualitative detection of the plasmid DNA of *Chlamydia trachomatis* and the genomic DNA of *Neisseria gonorrhoea* which is currently being used in clinical practice and clinical trials at our institution. This assay has shown high sensitivity and specificity for the detection of both organisms in asymptomatic and symptomatic patients. Youth who test positive for an STI will be referred to treatment. Youth will also be encouraged to refer sex partners for treatment. The county health department will be notified of reportable STIs. For analyses, sexually transmitted infection incidence will be defined as a positive laboratory test result for a new chlamydia or gonorrhea infection at any of the five assessment time points. Previous studies with ethnic minority youth have demonstrated feasibility and a high acceptance rate with respect to the collection of biological markers for determining STI incidence.

We would also like to collect data from clinic facilitators, clinic leaders, and physicians to assess organizational level factors and attitudes towards evidence-based interventions. To do this, we will use the below measures:

*Attitudes Towards Evidence-Based Practice Scale (EBP; facilitator; 15 items): this measure will be administered to facilitators to assess their views on evidence-based practices.*

*Multifactor Leadership Questionnaire (clinic leaders/physician, 21 items): this measure will be administered to clinic leaders/physicians to assess transformational and transactional leadership behavior.*

*Implementation Leadership Scale (ILS; Clinic leaders/physicians, 11 items): this measure assesses the degree to which organizational leaders support their staff in the implementation of evidence-based interventions*

*Implementation Climate Scale (clinic leaders/physician, 18 items): assesses the level of a strategic organizational climate within an organization.*

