This hypothesis will be analyzed using a univariate logistic regression for the binary outcome, new diagnoses of STIs (Yes/No). STI incidence will be defined as a positive laboratory test result for a new chlamydia or gonorrhea infection at any of the four follow up assessment timepoints. In the analysis for this hypothesis, condition will predict STI diagnosis. The test of the hypothesis will be based on a Wald test comparing the intervention regression coefficient to its standard error. Additionally, the time of STI diagnosis will be included as a covariate in the logistic regression to test the robustness of the intervention's effect.

**Power.** According to CDC national statistics, the annual STI incidence rate is 3.16% for Hispanic adolescents aged 15 to 19. Thus, we expect the 3-year STI incidence rate in the control group to be approximately 9.2%. Using a one-sided Z test with pooled variance to test the difference between two independent proportions (assuming the same 5% attrition rate at each assessment timepoint), the study has over 80% power to detect a difference of 6.1% in STI incidence between the two conditions. This difference in proportions translates to an effect size of Cohen's  $h = 0.26$ , considered a small ( $h = 0.2$ ) to medium ( $h = 0.5$ ) effect size, according to Cohen (1988).

**H2a:** *Intervention effects on frequency of drug use will be partially mediated by improvements in family functioning over time.*

To test for mediation, we will use the "product of coefficients" test described by MacKinnon and colleagues, which is based on the distribution of the indirect effect of the intervention through the mediator (Cohen, 1988). This procedure tests whether the product of the coefficients from the intervention to the mediator (a) and from the mediator to the outcome (b) is significantly different from zero. Specifically, we will estimate paths between intervention and family functioning (a), and between family functioning and drug use (b). Because we have five time points, our first mediation analyses will fit bivariate growth curves for both family functioning and drug use and examine the role of the (latent) slope of family functioning on the slope of

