drug use. The product of the two pathways  $(a) \times (b)$  is the indirect effect of eHealth Familias Unidas Primary Care to drug use through the family functioning trajectory. As noted above, we will be testing whether the product  $(a) \times (b)$  is statistically significantly different from zero, by comparing the observed value of  $(a) \times (b)$  to the empirical distribution calculated using the bias-corrected bootstrap. In addition to this long-term developmental mediation model, we will also test if the initial changes in family functioning from baseline to the 6 month follow-up mediate the effect of intervention on drug use trajectory. Our team has expertise in conducting mediational analyses in multilevel models.

Power. Mplus Monte Carlo simulation with 10000 replications was used to calculate the power for this hypothesis using a mediation model framework. With a final sample size of 370 (assuming 5% attrition rate at each assessment timepoint), we have 80% power to uncover a significant mediating effect when the regression coefficient of pathways 'a' is approximately -0.36 and 'b' is approximately -0.18 (i.e.,  $R^2$  effect size were 0.033 for the relationship between X and M (i.e., path 'a;') and M and Y (i.e., path 'b'), which is considered a small effect (Cohen, 1988).

***H2b: Intervention effects on frequency of unprotected sex will be partially mediated by improvements in family functioning over time.***

The analytic plan and power analysis for this hypothesis are similar to that of H1b.

***H2c: Intervention effects on STI incidence will be partially mediated by improvements in family functioning and decreases in unprotected sex over time.***

We will use MacKinnon's method described in H1b with the exception that the outcome for this hypothesis is binary. The Weighted Least Squares Means and Variance adjusted (WLSMV) estimator in Mplus will be used to estimate the indirect effect. With WLSMV, a continuous latent response variable ( $y^*$ ) underlying the observed dichotomous variable is used to test for the mediated or indirect effect.

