#### 15) **Risks to Subjects\***

We do not expect that there will be any negative consequences from participating in this study. However, the sensitive nature of some intervention topics (e.g. sexual behaviors and drug use) may be embarrassing and/or distressing to some participants. It is also possible that they may feel tired or fatigued after answering the questionnaires, or made uncomfortable by the questions that are asked. In addition, STI testing may involve minimal physical discomfort for the adolescent. Being tested for STIs may also cause anxiety for the adolescent and/or parent regardless of the adolescent's test results. Receiving positive results may make the adolescent and/or parent very upset. If the test is negative, there is still the possibility that the adolescent could be infected with an STI and test positive at some time in the future. Also, it is always possible that the test results could be invalid. Should an adolescent test positive for gonorrhea and/or chlamydia, the facilitator, with guidance from the clinical supervisor, a licensed clinical social worker, and principal investigator, will work with the adolescent on how to process disclosure of the positive test result to the parent or legal guardian. If after discussions with the facilitator and clinical supervisor, the adolescent still refuses to disclose (the law in FL does not require parents to be notified of STI infection) because s/he fears negative consequences such as being thrown out of the house or severe family discord, the facilitator and clinical supervisor will work with the adolescent to connect her/him to proper treatment. If an adolescent tests positive for an STI, we are required, by Florida law, to report the result to the Florida Department of Health.

If a parent or adolescent reports elevated levels of depression, or if an adolescent reports incidence of bullying, he or she will be directed to speak with a facilitator for further assessment. If necessary, a referral will be made for additional services.

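### H2c sets no time order between mediators and infection: under the only mediation method described, most infected youths contribute mediator values recorded after their positive test, which can bias path b

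*Combined protocol and SAP*

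**What the plan says.** Section 12(a) defines the STI outcome under H1c as a "positive laboratory test result for a new chlamydia or gonorrhea infection at any of the four follow up assessment timepoints", so it can occur from 6 months onward. H2c states that the effect on STI incidence is "partially mediated by improvements in family functioning and decreases in unprotected sex over time". Its method is the one said to be described in H1b, "with the exception that the outcome for this hypothesis is binary", estimated by WLSMV.

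H1b holds no mediation method; it refers back to the growth model of H1a. The only mediation method in the plan is under H2a. There, because there are five time points, "our first mediation analyses will fit bivariate growth curves for both family functioning and drug use", and path b relates one latent slope to the other. H2a adds a further model in which change in family functioning from baseline to 6 months mediates the effect on the drug use trajectory.

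The protocol also responds to a positive test. Section 10(c): "Youth who test positive for an STI will be referred to treatment", with encouragement to refer partners. Section 15: the facilitator, guided by the clinical supervisor and the principal investigator, "will work with the adolescent on how to process disclosure of the positive test result to the parent or legal guardian". That section foresees that an adolescent may refuse disclosure for fear of family discord.

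Nothing in H2c requires a mediator value to precede the infection, excludes values recorded after a positive test, or gives a sensitivity analysis for this.

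**The concern.** A mediation claim needs the mediator to come before the outcome. With slopes fitted to all five visits, a youth first positive at 6 months has three of five mediator values (12, 24 and 36 months) recorded after the result, one positive at 12 months has two, and one positive at 24 months has one. If the result changes behaviour or family relations, the outcome alters its own mediator.

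For unprotected sex, a fall after the result makes a steeper decrease go with having had an infection. Path b is then pulled toward zero or past it, even when unprotected sex truly causes infection. For family functioning, better communication after disclosure pulls path b toward reversal, while discord makes mediation look stronger than it is. A null, reversed or positive H2c result could not be read with confidence.

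**Working it through.** **1. The plan's own H2c figure.** The plan gives 80% power for a mediator coefficient of 0.63, OR 1.88, d = 0.35.
- OR = exp(0.63) = 1.88; d = 0.63 × √3/π = 0.35.
- Power = Φ(b√[n p(1−p)(1−ρ²)] − 1.96), with n = 370 (stated for H2a), p = (9.2% + 3.1%)/2 = 6.15% (from H1c) and ρ² = 0.033 (path a R² from H2a). The mediator SD of 1 and two-sided 5% test are assumptions, because H2c states neither.
- 0.63 × √(370 × 0.0615 × 0.9385 × 0.967) − 1.96 = 0.90, so power is 81.7%.

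The figure reproduces closely. It treats 0.63 as the effect of the mediator on infection, with no feedback.

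**2. How often mediator values follow the infection.** Input: 3.16% a year, held constant. Cumulative incidence is 1 − 0.9684^t.

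| Visit | Cumulative incidence | Share of 36-month infections first found by then |
|---|---|---|
| 6 months | 1.59% | 17% |
| 12 months | 3.16% | 34% |
| 24 months | 6.22% | 68% |
| 36 months | 9.18% | 100% |

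The last row matches the plan's 9.2%. Everyone first positive by 24 months who stays in the study has at least one later mediator value inside the slope: about two thirds. The 3.16% is for ages 15 to 19, while enrolment is at 12 to 16; if risk rises with age, infections come later and the share is lower.

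**3. How many infections carry path b.** 228 × 0.95⁴ = 185.7, which the plan takes as 185 per arm. 185 × (9.2% + 3.1%) = 22.8, so about 23 among 370. A few altered trajectories can matter.

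**4. Size of the bias, by simulation.** These inputs are assumptions, not document figures: visits at 0, 0.5, 1, 2 and 3 years; intercept variance 0.5; slope SD 0.3 per year; residual variance 0.35 (baseline SD √0.85 = 0.92); about 6% infected. Interval risk rises by 0.63 log-hazard per SD of unprotected sex at the previous visit. After a first positive, later values fall by a set amount. Path b is the logit of any infection on the 0 to 36 month slope, per SD; positive is the true direction.

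| Fall after a positive test | Slope alone | Slope with intercept |
|---|---|---|
| none | +0.17 | +0.31 |
| 0.25 SD | +0.02 | +0.17 |
| 0.5 SD | −0.10 | +0.04 |
| 1 SD | −0.37 | −0.24 |

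By linear interpolation the sign changes at 0.25 + 0.25 × 0.02/0.12 = 0.29 SD for the slope alone, and at 0.5 + 0.5 × 0.04/0.28 = 0.57 SD with the intercept. A probit version with about 9% control incidence crosses zero at about 0.54 SD for a true log OR of 0.63 per unit, and near 0.87 SD for a true log OR of 1.0. Hence 0.3 to 0.9 SD overall. With no true effect, falls of 0.25 to 1 SD give a false path b of −0.14 to −0.58.

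**5. Time-ordered versions.** In the first set-up, baseline-to-6-month change adjusted for baseline gives 0.27 to 0.30 per SD whether the later fall is 0, 0.25, 0.5 or 1 SD. In the probit set-up, the 0 to 12 month slope against infections first found at 24 or 36 months stays at +0.07 to +0.08 throughout (true log OR 0.63).

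**The case against.** **The criticised model is inferred.** This stands in part. The H1b reference is broken, and H2a's 6-month-change model, if carried over, would largely avoid the feedback. But that model is additional, is stated only for family functioning and drug use, and leaves out unprotected sex; infections found at 6 months would still be concurrent with it.

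**A reader might infer that the protocol acts on both mediators after every positive test.** The documents do not support that. Disclosure work bears on family functioning, and the adolescent may refuse to disclose. For unprotected sex the documents give treatment and partner referral only; no passage prescribes safer-sex counselling after a positive. The fall simulated above is therefore a plausible response, not a protocol action. Family functioning, the mediator that the protocol does touch, was not simulated.

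**A reader might infer that path b will come out reversed.** Reversal needs a substantial response and depends on the model; with the intercept included, a 0.5 SD fall still leaves path b slightly positive. Smaller responses only weaken it.

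**A reader might credit feedback with the whole gap between the slope coefficient and the 0.63 that generated the data.** That is wrong: the slope coefficient is only +0.17 or +0.31 with no response at all, which is a mismatch of slope and level. Only the change down the table is feedback. Nor does it prove much that a previous-visit model recovers 0.63 when infections were generated from the previous visit's value.

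**The stakes are limited.** True: H2c is secondary, and the primary STI test, H1c, is unaffected.

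**Conclusion.** The concern holds in this form. H2c does not state its mediator window, and the lead model of the only method it could borrow lets mediator values recorded after the infection enter path b, while the protocol itself responds to a positive test. About two thirds of infected youths would be affected at a constant 3.16% a year. For unprotected sex, assumed falls of 0.25 to 1 SD shrink path b, with a change of sign at about 0.3 to 0.9 SD depending on the model. For family functioning the direction is open. These sizes rest on assumed variances and assumed responses; the missing time order does not. The sponsor should fix this before analysis, but it does not threaten the primary endpoints.

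**What to change.** In section 12(a), correct the H1b cross-reference and write out the H2c model so that only mediator values measured before the first positive test enter path b. Either form would do:
- relate baseline-to-6-month change in family functioning and in unprotected sex, adjusted for baseline, to infections first found after 6 months; or
- fit a discrete-time model of each visit's result, up to the first positive, on condition, visit and previous-visit mediator values.

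Estimate path a in a separate model of each mediator on condition over the same pre-infection window; the infection model gives path b only. Keep the full-slope model as a sensitivity analysis. Also reconcile the four follow-ups in section 12(a) with section 10(c), which counts an "infection at any of the five assessment time points".

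The cost is SAP wording and code; the data are already planned. The downside is that infections found at 6 months are lost to the mediation test or contribute little. Under the first form about 23 × (1 − 0.17) = 19 remain, so the detectable coefficient rises from 0.63 to roughly 0.63 × √(23/19) = 0.69. Under the second, the 24- and 36-month results rest on a 90-day behaviour report taken 12 months earlier, so much of the exposure interval is unmeasured. Restate the H2c power accordingly.

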Power. We aimed to identify the minimal detectable regression coefficient for the mediator based on Vittinghoff and colleagues' methodology. The results show that we have 80% power to detect a mediating effect if the logistic regression coefficient for the mediator is 0.63, which is equal to an OR of 1.88, corresponding to an effect size of  $d = 0.35$ . According to Cohen, this is considered a small ( $d = 0.2$ ) to medium ( $d = 0.5$ ) effect size.

(b) Secure Data and Quality Control

All adolescent and parent self-report measures will be administered electronically through a tablet.

Data will be uploaded weekly in a database housed on a server maintained and secured by the University of Miami Department of Public Health Sciences. The server is password protected as well as protected by a firewall. The Principal Investigator will have access to the data electronically on his password protected laptop. His designees (i.e. Project Coordinator and Statistician) will also have access to electronically stored data. Principal Investigator and his team are on the tenth floor of the Clinical Research Center at [name].

We will also collect identifying data (e.g. participant name and contact information). This data will be collected electronically and stored in secure University of Miami systems. We will use a record system in which all participant records are filed numerically by case number, with no identifying information attached to the outcome data. A master sheet, with individual names and their respective code numbers will be kept electronically and accessed only under the supervision of the Principal Investigator. No one other than the Principal Investigator, the Project Coordinator, and approved study staff will have access to records identifying subjects' names at any time. Only the Principal Investigator and the Project Coordinator (under the supervision of the Principal Investigator) will have access to both the participants' identifying information and their assessment data.

(c) Data and Specimen

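### H2c power: the d = 0.35 label treats a coefficient of 0.63 as a two-group contrast; on the per-SD reading that reproduces 80% power, the two-group-equivalent d is about 0.6 to 0.7

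*Combined protocol and SAP*

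**What the plan says.** The H2c power paragraph in section 12(a) names its method: "We aimed to identify the minimal detectable regression coefficient for the mediator based on Vittinghoff" and colleagues' approach. It then reports: "The results show that we have 80% power to detect a mediating effect", on the condition given as "if the logistic regression coefficient for the mediator is 0.63, which is equal to an OR of 1.88, corresponding to an effect size of", where the value that follows is d = 0.35. It rates this value: "According to Cohen, this is considered a small" (d = 0.2) to medium (d = 0.5) effect. The paragraph gives no unit or SD for the mediator, and no N, alpha, incidence or correlation between condition and mediator.

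The hypothesis is that the STI effect is "partially mediated by improvements in family functioning and decreases in unprotected sex over time". Under section 10(c), family functioning is built from multi-item scales and sexual risk behaviour is recorded as numbers of occasions. For H2a, the plan will "examine the role of the (latent) slope of family functioning" on the slope of drug use, so there the mediator is a continuous latent quantity. H2a's power statement is in variance explained: "effect size were 0.033 for the relationship between X and M", with the same value for the path from mediator to outcome, called a small effect.

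**The concern.** Multiplying a log odds ratio by √3/π gives a standardised mean difference when the odds ratio compares two groups. Applied to a slope on a scale score or a frequency, it gives something else: the shift in the latent response per unit of the mediator. Cohen's 0.2 and 0.5 are benchmarks for two-group differences, and the plan applies them to this number.

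At stake is what H2c can show. A reader of section 12(a) would conclude that the trial can detect a mediator effect on STI between small and medium, not far from the small effect claimed for H2a. If the detectable effect is about twice the label, a non-significant H2c says much less about mediation than that reader would suppose.

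**Working it through.** **Inputs**
- b = 0.63, power 80%, d = 0.35: H2c power paragraph.
- N = 370: stated for H2a, assumed here.
- Incidence p = 6.15%: H1c gives 9.2% in controls and a detectable difference of 6.1 points, hence 3.1% with the intervention; (9.2 + 3.1)/2 = 6.15.
- ρ², squared correlation of condition and mediator: 0.033 is stated for H2a. I also show 0 and 0.073 (ρ = 0.27).
- Two-sided 5%: assumed. H2c gives no alpha or sidedness; H1c uses a one-sided test.

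**1. The plan's conversions reproduce.** exp(0.63) = 1.88 and 0.63 × √3/π = 0.347.

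**2. The plan's 80% reproduces per SD.** Formula: power = Φ(b × SD × √[N p(1−p)(1−ρ²)] − 1.96). Here N p(1−p) = 370 × 0.0615 × 0.9385 = 21.36.

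| ρ² | √[N p(1−p)(1−ρ²)] | Minimum b per SD = 2.80/root | Power at 0.63, SD = 1 | Power at 0.63, 50:50 binary (SD = 0.5) |
|---|---|---|---|---|
| 0 | 4.62 | 0.606 | 83% | 31% |
| 0.033 | 4.54 | 0.616 | 82% | 30% |
| 0.073 | 4.45 | 0.630 | 80% | 29% |

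A simulated logistic Wald test (N = 370, p = 6.15%, ρ = 0.27) gave 77% at b = 0.63.

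**3. A binary mediator does not reproduce it.** A 50:50 split has the largest SD of any binary variable, so it is the most favourable case. For 80% power at 0.63 it needs p(1−p) = (2.80/0.315)²/370 = 0.214, an incidence of about 31% (about 22% with N = 456), against a stated 9.2% or less. Over N of about 370 or 456, incidence of 3.1%, 6.15% or 9.2%, and one- or two-sided 5%, its power peaks at 62%: N = 456, p = 9.2%, one-sided, ρ = 0, where 0.315 × √38.09 − 1.645 = 0.30.

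**4. What 0.63 per SD means as a two-group d**
- Mediator difference between infected and uninfected youths: d = bσ, where σ² is the within-group variance and solves σ² = 1 − p(1−p)b²σ⁴. With p(1−p)b² = 0.0577 × 0.397 = 0.0229, σ² = 0.978 and d = 0.63 × 0.989 = 0.62. Simulation gave 0.62.
- Latent-response scale: R² = 0.397/(0.397 + π²/3) = 0.108, r = 0.328, and d = 2r/√(1−r²) = 0.69.

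**5. Power for the mediator–outcome path at smaller effects.** Holding 80% at b = 0.63 removes the dependence on N, p and ρ: power = Φ(2.80 × b/0.63 − 1.96) two-sided, or Φ(2.49 × b/0.63 − 1.645) one-sided.
- Mediator difference of 0.35 (b about 0.35): 34% two-sided, 40% one-sided. With the inputs of step 2 instead, 34–37% two-sided. Simulation gave 32.5%.
- d = 0.35 defined through r: b = 0.35 × π/(2√3) = 0.317, power 29% two-sided.
- H2a's R² of 0.033: b = √(0.033/0.967 × 3.29) = 0.335 (OR 1.40), power 32–34% two-sided over the three rows of step 2.

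**The case against.** The strongest reply is that the power claim is tied to b = 0.63, and that claim reproduces. A reader might infer from step 5 that H2c has only about 35% power where the plan says 80%. The documents do not support that: at the coefficient stated, 80% stands. The figures in step 5 apply to a smaller effect and to a single-path Wald test. The planned test is of an indirect effect estimated by WLSMV, and its power is not calculated here.

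Second, 0.35 has a coherent meaning. It is the shift in the latent response, in residual SDs, per SD of the mediator, and the plan does analyse H2c on a latent-response scale. So the multiplication is not an arithmetic slip. What fails is the rating, because a standardised slope is not a two-group difference and the quoted benchmarks are for the latter.

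Third, the per-SD unit is a reconstruction, with N and incidence borrowed and alpha assumed. An exact 0.630 needs ρ of about 0.27, which the documents do not give, and other inputs move the result: N = 456 with two-sided 5% and p = 6.15% gives 90% at ρ = 0 and 80% at ρ = 0.5. This stands as a limit on certainty. It does not rescue the two-group reading, which falls short of 80% throughout the range examined.

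Fourth, whether the effect is above medium depends on the metric. By d it exceeds 0.5. By f² = 0.108/0.892 = 0.12, for which the plan gives no benchmark, the wording might be defended. Frequency of unprotected sex may also be mostly zeros: in the earlier school effectiveness trial described in section 4(b), 130 of 746 youths were sexually active in the 90 days before any assessment. A d computed for a roughly normal mediator is then only approximate.

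**Conclusion.** The point holds as a mislabelled detectable effect. On the plan's own sample size and incidence, 80% power at 0.63 and a two-group d of 0.35 cannot both be true. The reading that fits is 0.63 per SD of the mediator, equivalent to a two-group d of 0.62 (mediator difference by infection status) to 0.69 (through r), with R² about 0.11. That is 1.8 to 2 times the stated d, and over three times the R² used for H2a (0.108/0.033 = 3.3). Power for the mediator–outcome path is about 29–40% at a mediator difference of d = 0.35, depending on sidedness and the definition of d, and about one third at H2a's R².

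This rests on N = 370, about 6% events, an assumed alpha of 5% and an inferred unit. It is not a finding that the trial is under-powered at its stated coefficient, nor that the conversion was miscalculated. Since STI mediation is a secondary endpoint, the consequence is confined to how H2c is described and how a null result is read.

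**What to change.** In the H2c power paragraph of section 12(a):

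1. Confirm the unit and SD of the mediator behind 0.63, and state N, alpha and sidedness, STI incidence and the assumed correlation between condition and mediator.
2. If the unit is confirmed as one SD, replace the d = 0.35 label and its rating with: OR 1.88 per SD of the mediator (latent-response R² about 0.11; two-group-equivalent d about 0.6 to 0.7). If another unit was meant, state it and recompute.
3. Add that power for this path at the R² of 0.033 used for H2a is about one third, so a non-significant H2c is inconclusive about mediation. Say that these figures are for the single mediator–outcome path and not for the WLSMV indirect-effect test.

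The cost is a reworded sentence and a short list of inputs. The stated detectable effect becomes less favourable. Sample size, data collection and conduct are unchanged.
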